Data collection will be performed via pain scores obtained prior to and following placement of the regional anesthetic and establishment of analgesia, along with data on maternal satisfaction. Electronic medical records will also be used to gather the resulting outcomes.

Data to be collected:

Demographics:

- age
- weight
- height
- ethnicity
- gestational age
- reason for previous cesarean/incision type if known
- previous SVD
- pregnancy number
- cervical dilation at/near time of block (performed by obstetrician)
- estimated fetal weight

Pain scores:

- before RA
- 15 minutes, 30 minutes, and 60 minutes after RA
- 24 hours after delivery

Supplementation of catheter boluses for pain relief and total doses given

Side effects of RA:

- pruritus
- nausea
- vomiting
- hypotension
- post dural puncture headache

Neonatal outcome:

- fetal heart rate immediate post regional
- APGARs at 1 min and 5 min

- birth weight

Delivery:

- date and time at which cervix becomes fully dilated (performed by obstetrician)
- date and time at which the following occur:
 - SVD
 - c-section
 - instrumentation

Maternal Satisfaction

- pain relief
- childbirth experience

Data Analysis Plan:

Power Analysis

Our null hypothesis is that there is no difference in success of VBAC between epidurals and CSEs for women undergoing TOLAC. Our alternative hypothesis is that CSE will result in more successful VBAC than will epidurals. The success rate of VBAC is around 74%. Based on the literature, we expect the success rate with CSE to increase by 20-25%; therefore, given our sample size of 60, we will have 80% power to detect a difference between the two groups.

Primary Outcome

The primary outcome, success for VBAC, will be assessed using χ^2 or the Fisher Exact test, in case of cell sizes <5, to determine if the difference in success rates between the two analgesia groups, CSE and epidural, is statistically significant. Logistic regression analysis will be used to adjust for potential confounders and other factors associated with success or failure of VBAC.

Secondary Outcomes

The secondary outcome, success of analgesia, as measured by pain score on a scale of 1 to 10, will be assessed using ANOVA. Difference in mean pain score between the two groups will be determined in a model with the continuous/count variable pain score as the dependent variable and analgesia group as the independent variable.

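### At alpha 0.05, 60 patients do not give 80% power across the stated 20–25% increase under either sidedness, and the plan states neither alpha nor sidedness

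*Combined protocol and SAP*

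**What the plan says.** All the relevant text is in the Data Analysis Plan.

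- Null (Power Analysis): "Our null hypothesis is that there is no difference in success of VBAC between epidurals and CSEs for women undergoing TOLAC".
- Alternative (Power Analysis): "Our alternative hypothesis is that CSE will result in more successful VBAC than will epidurals".
- Power (Power Analysis): after citing a success rate of about 74% and an expected rise of 20–25% with CSE, the plan states that "given our sample size of 60, we will have 80% power to detect a difference between the two groups".
- Test (Primary Outcome): VBAC success "will be assessed using χ^2 or the Fisher Exact test, in case of cell sizes <5", in order "to determine if the difference in success rates between the two analgesia groups, CSE and epidural, is statistically significant".

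No alpha and no sidedness appears anywhere in the document, for the power statement or for the test. The plan does not say whether the rise is in percentage points or relative to 74%. Nor does it state the allocation ratio or an allowance for dropout.

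**The concern.** A power claim can be checked only when alpha, sidedness, effect size and test are fixed. Here the first two are missing and the third is a range that can be read in two ways. The directional alternative makes a one-sided calculation a possible reading, and the other sentences point to a two-sided one. So the first question is whether 80% holds under any ordinary reading.

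Two things are at stake. If true power is well below 80%, a non-significant result from this pilot may be taken as evidence against a CSE effect that the trial had little chance of detecting. And while sidedness is unwritten, the choice can be made after the data are seen. Chi-square has no direction, but Fisher's test has one- and two-sided forms. Fisher is the test that would nearly always apply at the planned effect.

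**Working it through.** **Inputs from the plan.** Epidural success rate 0.74. CSE rate after a 20–25% rise: 0.74 + 0.20 = 0.94 to 0.74 + 0.25 = 0.99 if absolute; 0.74 × 1.20 = 0.888 to 0.74 × 1.25 = 0.925 if relative. Total 60. Fisher if a cell is below 5, otherwise chi-square.

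**Assumptions.** 1:1 allocation (n = 30 per arm), no dropout, alpha 0.05 (0.025 to 0.10 also tried).

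**Step 1: try to reproduce 80% with the usual formula.** Power = Φ[(d − z·s0)/s1], where d = p2 − p1, p̄ is the mean of the two rates, s0 = √[2p̄(1 − p̄)/n], s1 = √{[p1(1 − p1) + p2(1 − p2)]/n}, and z = 1.960 two-sided or 1.645 one-sided.

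- +20 points: s0 = √(2 × 0.84 × 0.16/30) = 0.0947; s1 = √[(0.1924 + 0.0564)/30] = 0.0911. Two-sided: (0.20 − 1.960 × 0.0947)/0.0911 ≈ 0.16, power 0.563. One-sided: ≈ 0.49, power 0.687.
- +25 points: s0 = √(2 × 0.865 × 0.135/30) = 0.0882; s1 = √[(0.1924 + 0.0099)/30] = 0.0821. Two-sided: ≈ 0.94, power 0.826. One-sided: ≈ 1.28, power 0.899.

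A figure near 80% appears under several combinations: one-sided 0.05 at +22.5 points (0.804), one-sided 0.10 at +20 points (0.806), and two-sided 0.05 at +25 points (80% needs 29 per arm, 58 in all). The plan does not say which, if any, was used, so there is no single figure to reproduce.

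**Step 2: exact power of the planned test.** Power = Σ Σ Bin(a; 30, p2) · Bin(b; 30, 0.74), summed over all tables with p ≤ 0.05. Here p comes from Fisher if any observed count is below 5 and from uncorrected chi-square otherwise. At 74% vs 94% some cell is below 5 in 97% of trials, so this is nearly Fisher's test.

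| CSE rate | Exact, two-sided | Exact, one-sided | Approx., two-sided | Approx., one-sided |
|---|---|---|---|---|
| 0.94 (+20 points) | 0.42 | 0.55 | 0.56 | 0.69 |
| 0.99 (+25 points) | 0.75 | 0.86 | 0.83 | 0.90 |
| 0.888 (× 1.20) | 0.21 | 0.31 | 0.31 | 0.43 |
| 0.925 (× 1.25) | 0.35 | 0.47 | 0.48 | 0.61 |

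Reading the cell-size rule as expected rather than observed counts gives 0.49 and 0.75 two-sided, 0.61 and 0.86 one-sided, for +20 and +25 points. The pattern is the same.

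**Step 3: what unwritten sidedness does to a verdict.** At 0.05 for both versions, Fisher applies to each of these tables:

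| CSE | Epidural | p two-sided | p one-sided |
|---|---|---|---|
| 28/30 | 22/30 | 0.080 | 0.040 |
| 27/30 | 20/30 | 0.057 | 0.029 |
| 29/30 | 23/30 | 0.052 | 0.026 |

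The two versions disagree in 13.1% of trials at 74% vs 94%, and in 10.9% at 74% vs 99%. With no effect at 74%, false significance in favour of CSE occurs in 1.8% of trials two-sided and 4.0% one-sided. All of this compares two-sided 0.05 with one-sided 0.05. At one-sided 0.025 the CSE-favouring verdicts agree with the two-sided rule and the gap all but vanishes.

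**The case against.** The strongest reply is that the plan is an ordinary two-sided one. Null, test and power sentence all speak of a difference, and the directional alternative reads naturally as the investigators' expectation. Stating an expected direction and testing two-sided is common practice. That stands. A reader might infer that the written rules contradict one another, but the text does not support this: one sentence names a direction, the other three do not, and nothing mentions a one-sided p-value. What is missing is a written alpha and sidedness.

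A reader might also infer that 80% can be reached only with a one-sided test. That is not so. By the normal approximation, two-sided power at +25 points is 0.826, so the plan's figure is compatible with a routine two-sided calculation at the top of the range.

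Three further points are fair. The 13% disagreement rate depends on taking one-sided alpha as 0.05. The example tables reflect Fisher's conservatism as well as sidedness: uncorrected two-sided chi-square would give 28/30 vs 22/30 p = 0.038. And this is a self-described pilot, which lowers the stakes.

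None of this rescues the power claim. The plan attaches 80% to a range of effects, and the low end fails under either sidedness at 0.05. The pilot label does not remove a stated power and a significance test on the primary outcome.

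**Conclusion.** The concern holds as a power claim that is wrong as written, together with an unstated alpha and sidedness. At alpha 0.05 with 30 per arm and no dropout, power at +20 points is 42% exact or 56% approximate two-sided, and 55% or 69% one-sided. None reaches 80%. At +25 points the planned test two-sided still reaches only 75%; one-sided it reaches 86%. The relative reading is lower throughout.

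Sidedness is not the largest source of uncertainty. It moves power by about 7 to 13 points on the absolute reading, whereas moving from +20 to +25 points moves it by 21 to 33 points (for example 0.899 − 0.687 = 0.21 and 0.747 − 0.422 = 0.33). Writing down alpha and sidedness alone would therefore not repair the claim.

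The conclusion rests on alpha 0.05. One-sided 0.10 would give 0.806 at +20 points by the approximation, but the document offers no support for that level, and the exact power of the planned rule there is 0.73. Unequal allocation or dropout would be expected to lower power further.

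**What to change.** In the Data Analysis Plan:

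1. Word the alternative as: VBAC success differs between CSE and epidural.
2. State that the chi-square/Fisher test of the primary outcome is two-sided at alpha 0.05, and use the same basis for the power statement.
3. Say whether the 20–25% increase is absolute or relative.
4. Replace the 80% figure with the power of the planned test at both ends of the range: about 42% to 75% if absolute, about 21% to 35% if relative, with 30 per arm and no dropout stated as assumptions.

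This takes a few sentences and changes neither enrolment nor procedures. It should be done before outcome data are seen. The cost is that the stated power becomes less favourable, and the pilot has to be presented as unlikely to detect the lower end of the expected effect.

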**Outcomes of Epidural versus Combined Spinal and Epidural (CSE) Anesthetic
Technique on the Success of Trial of Labor after Cesarean (TOLAC): A pilot study**

NCT02105558

Version Date: 03/24/2014

Department of Anesthesiology

Scholarly Research Project Submission Form

Name(s): [name] (PI), [name], FRCA (co PI)

Faculty Mentor: [name], FRCA

Category of Research: Prospective randomized clinical pilot study

Expected length of time for Project: One year or until 60 patients have been enrolled

Title of Research Project: Outcomes of Epidural versus Combined Spinal and Epidural (CSE) Anesthetic Technique on the Success of Trial of Labor after Cesarean (TOLAC): A pilot study

Summary of Project: To compare the effects of epidural versus CSE anesthesia on the success of TOLAC. This will be a prospective clinical study randomizing 60 eligible women into either an epidural group or CSE group. The effects of the specific regional anesthetic on patient's individual labor efforts will then be closely monitored. Written informed consent shall be obtained to enroll the patients in either group. Pain scores and electronic medical record information will be used with non-identifiable coding to determine the resulting outcomes.

Background:

Though it has been said, "once a cesarean, always a cesarean," the current medical stance has changed and now encourages VBAC in a select population of patients. VBAC has several advantages over a repeat cesarean including decreased recovery period, decreased risk of infection, avoidance of major abdominal surgery, and lessened blood loss (1). Predictors for success of VBAC include previous spontaneous vaginal birth, singleton pregnancy, and previous low transverse scar for C-section delivery (1). TOLAC is a reasonable option for select pregnant women and is associated with a 74% likelihood of VBAC (3). Risk factors for failure of VBAC include labor dystocia, advanced maternal age, maternal obesity, fetal macrosomia, GA>40 weeks, short inter pregnancy interval, and preeclampsia (1).

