While success of VBAC is associated with fewer complications, failure of VBAC may be associated with increased complications (1). A major concern for VBAC is the possibility for uterine rupture, which may result in hysterectomy and intrapartum fetal hypoxia/death. According to the ACOG guidelines, effective regional analgesia should not be expected to mask the signs and symptoms of uterine rupture, particularly because the most common sign of rupture is fetal heart tracing abnormalities. Adequate

pain relief achieved with either CSE or epidurals may even encourage more women to opt for VBAC. The decision to proceed with TOLAC should occur only after appropriate discussion of the risks and benefits has occurred between the patient and her obstetrician and as long as no other contraindications exist. The final decision should be left up to the patient. There is no reliable way to predict risk of uterine rupture, but it may be associated with classical and low vertical uterine scars, induction of labor, and increased number of prior cesarean deliveries and risk may be decreased by previous vaginal birth (3). Other aspects of VBAC versus repeat cesarean pertaining to the fetus to consider include respiratory function, mother-infant contact, and initiation of breastfeeding, which may be delayed in cesarean deliveries (3).

There is very little research concerning the effects of CSEs and epidurals on women undergoing TOLAC. There have been multiple studies comparing CSE and epidurals on nulliparous and multiparous women, but none have been done specifically on patients undergoing TOLAC. There is only one study comparing CSEs and epidurals in the general population demonstrating similar rates of hypotension and hemodynamic responses in 80 patients undergoing total knee replacement (8). According to the ASA practice guidelines for obstetric anesthesia "nonrandomized comparative studies suggest that epidural analgesia may be used in a trial of labor for previous cesarean delivery patients without adversely affecting the incidence of vaginal delivery. Randomized comparison of epidural versus other anesthetic techniques were not found." They agree that neuraxial techniques improve the likelihood of vaginal delivery for patients attempting VBAC and suggest neuraxial catheter be placed in event of operative delivery (9). Because no study to date has compared CSEs and epidurals and their effects on the success of VBAC, we would like to further investigate this arena.

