Inclusion criteria: (all patients meeting ACOG guidelines for TOLAC) ASA II Patients 18 years of age or more with at least one previous elective cesarean delivery, <40 weeks gestational age (GA), vertex singleton pregnancy with use of continuous fetal monitoring.

Exclusion criteria: Patients undergoing TOLAC but refusing regional anesthetic or with contraindication for regional anesthesia, less than 18 years of age, BMI >40 or with associated comorbidities such as gestational diabetes, preeclampsia, abnormal placenta, etc.

Specific outcomes to be looked at include:

Primary outcome:

- Success of vaginal birth after cesarean (VBAC)

Secondary outcomes:

- Success of analgesia/ maternal satisfaction (self- rated pain score of 1-10 prior to, 30 minutes after the regional anesthetic is performed and 24 hrs post-delivery)
- If requiring a repeat C-section or instrumental delivery the success of regional anesthesia for the procedure. (self- rated pain score of 1-10 and necessity to use additional IV pain medication or conversion to general/ spinal anesthesia)
- Immediate side effects: fetal bradycardia, nausea, vomiting, pruritus, hypotension requiring vasopressors
- Late side effects i.e. post dural puncture headache

Methods:

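### The single 80% power claim at 60 women does not hold across the plan's own 74% plus 20-25% assumption, and neither assumed figure is shown to apply to this trial

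*Combined protocol and SAP*

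**What the plan says.** The Power Analysis (Data Analysis Plan) puts VBAC success at around 74% and continues: "Based on the literature, we expect the success rate with CSE to increase by 20-25" percent. It concludes that "given our sample size of 60, we will have 80% power to detect a difference between the two groups". It does not give alpha, sidedness, the allocation ratio or whether the increase is absolute or relative. The alternative hypothesis is directional, in favour of CSE. The Primary Outcome section names chi-square, or Fisher's exact test when cell sizes fall below 5.

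On the source of the two figures:

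- **The 74%.** The Background says that TOLAC in select pregnant women is "associated with a 74% likelihood of VBAC". This is not a rate by type of analgesia.
- **The effect.** The Background says that "no study to date has compared CSEs and epidurals and their effects on the success of VBAC". It mentions comparisons in nulliparous and multiparous women but quotes no effect on delivery from them.
- **The population.** The Background states: "Risk factors for failure of VBAC include labor dystocia, advanced maternal age, maternal obesity, fetal macrosomia, GA>40 weeks, short inter pregnancy interval, and preeclampsia". Inclusion requires less than 40 weeks' gestation. Exclusions include "BMI >40 or with associated comorbidities such as gestational diabetes, preeclampsia, abnormal placenta, etc".

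**The concern.** One power figure is attached to a range of effects, and power changes steeply over that range. A success rate of 94-99% in about 30 women means very few CSE failures, so the conservative Fisher test will usually apply. Power from the usual normal approximation will then be too high.

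The inputs are also weakly anchored. An effect said to come from the literature sits beside a statement that nobody has studied it for this outcome. A general TOLAC rate stands in for the epidural arm of a more restricted group. With success already near three in four, there is little room above the reference rate, so a modest error in it matters.

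At stake is how the result is read. If 80% power is taken at face value, a non-significant difference looks like evidence against an established effect. It would in fact be an expected outcome of a small study.

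**Working it through.** **Inputs.** From the plan: N = 60, reference rate 74%, increase 20-25%, chi-square or Fisher if a cell is below 5. Assumed because not stated: 30 per arm, alpha 0.05, no dropout, and both one- and two-sided tests. On the absolute reading CSE is 94-99%. On the relative reading it is 0.74 × 1.20 = 88.8% to 0.74 × 1.25 = 92.5%.

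**Step 1: reproduce the 80%.** Normal approximation, with n per arm and p̄ the mean of the two rates:

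power = Φ{ [ |p2 − p1|√n − z√(2p̄(1 − p̄)) ] / √(p1(1 − p1) + p2(1 − p2)) }

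- 74% v 96.5% (+22.5 points), one-sided: (1.232 − 0.825)/0.476 = 0.857, power 80.4%.
- 74% v 99%, two-sided: (1.369 − 0.947)/0.450 = 0.939, power 82.6% (29 per arm needed for 80%).
- 74% v 94%, two-sided: (1.095 − 1.016)/0.499 = 0.159, power 56.3%. One-sided: 68.7%.

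So the stated figure can be reproduced at the middle or top of the range, but not at the bottom.

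**Step 2: power of the planned test.** Sum over all 31 × 31 possible results (a epidural successes, b CSE successes):

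power = Σ Σ Bin(a; 30, p1) × Bin(b; 30, p2) × 1[p-value(a, b) ≤ 0.05]

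The p-value is Fisher's if any observed cell is below 5, otherwise uncorrected chi-square. Expected CSE failures are 30 × 0.06 = 1.8 down to 30 × 0.01 = 0.3, so Fisher nearly always applies.

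| Epidural v CSE | Reading | Two-sided | One-sided |
|---|---|---|---|
| 74 v 94 | +20 points | 42.2% | 55.3% |
| 74 v 99 | +25 points | 74.7% | 85.6% |
| 74 v 88.8 | +20% relative | 20.7% | 30.8% |
| 74 v 92.5 | +25% relative | 34.7% | 47.2% |

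If the cell-size rule refers to expected counts, two-sided power is 48.8% at +20 points and 75.3% at +25.

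**Step 3: the ceiling, if the epidural rate is above 74% (assumed).** Let CSE succeed in all 30 women. One cell is then 0 and Fisher applies. Against 30/30, the two-sided p-value is 0.024 for 24/30 epidural successes and 0.052 for 25/30. Two-sided power is therefore P(Bin(30, p1) ≤ 24). The one-sided p-value is 0.026 for 25/30 and 0.056 for 26/30, so one-sided power is P(Bin(30, p1) ≤ 25).

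| Epidural rate | Maximum power, two-sided | Maximum power, one-sided |
|---|---|---|
| 74% (plan) | 83.0% | 92.1% |
| 75% (assumed) | 79.7% | 90.2% |
| 78% (assumed) | 67.4% | 82.1% |
| 79% (assumed) | 62.5% | 78.5% |
| 80% (assumed) | 57.2% | 74.5% |

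**Step 4: which way might the 74% be off?** Eligibility removes three items on the plan's list of failure factors, in whole or in part: late gestation, preeclampsia, and obesity only above BMI 40. It does not exclude advanced maternal age, macrosomia, a short interval or BMI up to 40, and it does not require a previous vaginal birth. A higher rate is plausible, but its size cannot be derived from the documents.

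**The case against.** The strongest reply is that the 80% is not an arithmetic error. It can be reproduced by standard formulas near the middle or top of the range, and the planned rule itself gives 86% one-sided at +25 points. The directional alternative makes a one-sided reading arguable. That stands, but it supports 80% only at one end, on one choice of sidedness and on the absolute scale, and the plan states none of these choices. At +20 points no variant tried reaches 80%. Even uncorrected chi-square throughout gives 59.8% two-sided and 73.2% one-sided.

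A reader might go further and infer three things that the documents do not support:

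- **That the plan contradicts its own 74%.** It does not. The figure already concerns select women, no other rate is given, and several failure factors remain eligible.
- **That the effect is impossible, or 80% power unreachable whatever CSE does.** At 74%, a CSE rate of 94-99% is possible and maximum two-sided power is 83%. The point at which 80% becomes unreachable also depends on the test: an epidural rate of about 75% for two-sided Fisher, 79% for one-sided Fisher, and 83% for two-sided uncorrected chi-square. On a relative scale the arithmetic ceilings are 80% (+25%) and 83.3% (+20%), against 75% and 80% for percentage points.
- **That no literature could lie behind the effect.** The Background denies only a comparison on VBAC success. Extrapolation from other labouring women is possible, though the plan neither cites nor quotes any such figure for the effect.

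Finally, the study is called a pilot, and 60 may be a sensible pilot size. That is a reason not to ask for more women. It does not justify an unqualified power claim.

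**Conclusion.** The point holds as a defect in the stated power and its justification. Under the planned test with two-sided alpha 0.05 and 30 per arm, power never reaches 80% within the plan's range: it runs from 42% to 75% on the absolute reading and from 21% to 35% on the relative reading. A one-sided test reaches 80% only near the top of the absolute range (55% to 86%) and nowhere on the relative one (31% to 47%). These figures rest on assumed equal allocation, alpha and no dropout.

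The effect has no cited source and no direct evidence on VBAC by the plan's own account. The 74% is not shown to apply to eligible women given an epidural. The loss of power from a higher epidural rate is a conditional risk: it depends on a rate that the documents do not give.

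**What to change.** Reword the Power Analysis:

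1. Call the 74% and the 20-25% increase planning assumptions. Say that the 74% comes from TOLAC in select women, and that any support for the effect is extrapolated from other labouring women.
2. State alpha, sidedness, allocation ratio, and whether the increase is in percentage points or relative.
3. Replace the single 80% with the power of the planned test at both ends of the effect range, and over a range of epidural rates labelled as assumed.
4. Report the difference in VBAC rates with its 95% CI, and state in advance that a non-significant result is inconclusive.

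The cost is a less favourable stated power. No extra women, visits or data are needed, and reporting an estimate with its interval suits a pilot.

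### The single 80% power figure does not hold across the stated 20-25% gain: at 74% versus 94% with 30 women per arm, power is 42-73% at a 5% level

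*Combined protocol and SAP*

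**What the plan says.** The Summary of Project describes "randomizing 60 eligible women into either an epidural group or CSE group". The Power Analysis paragraph of the Data Analysis Plan gives the inputs:

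- Baseline: "The success rate of VBAC is around 74" per cent.
- Effect: "Based on the literature, we expect the success rate with CSE to increase by 20-25" per cent.
- Direction: "Our alternative hypothesis is that CSE will result in more successful VBAC than will epidurals".
- Conclusion: "given our sample size of 60, we will have 80% power to detect a difference between the two groups".

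The Primary Outcome paragraph then names the test: chi-square, or "the Fisher Exact test, in case of cell sizes <5".

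The plan does not state the significance level, whether the test is one- or two-sided, the allocation ratio, any dropout allowance, whether the gain is in percentage points or relative, or whether the switch to Fisher depends on observed or expected counts. On the source of the effect size, the Background says there are "multiple studies comparing CSE and epidurals on nulliparous and multiparous women, but none have been done specifically on patients undergoing TOLAC".

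**The concern.** With 30 women per arm, power changes steeply between a 20-point and a 25-point gain, so one figure cannot describe both ends. The top of the range is also extreme: at 99% success only 30 × 0.01 = 0.3 failures are expected in the CSE arm. Success rates this high make small cells almost certain, so the plan's own rule leads to Fisher's exact test. A chi-square power formula would then overstate the power of the test actually run.

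A reader would naturally take the sentence to mean that a true 20-point gain would be missed about one time in five. If the real chance of missing it is closer to one in two, a non-significant pilot result says much less than it appears to, and a follow-on trial sized from the same reasoning would be too small.

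**Working it through.** **Inputs.** From the Power Analysis: baseline p1 = 0.74, gain 20-25%, total 60, power 80%. Absolute reading: p2 = 0.94 to 0.99. Relative reading: p2 = 0.74 × 1.20 = 0.888 to 0.74 × 1.25 = 0.925. Assumed because not stated: 30 per arm, 5% level, no dropout. The 74% is an overall TOLAC figure; it is taken here as the epidural-arm rate, as the plan's comparison implies.

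**Where 80% can be reproduced.** The usual normal formula is

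power = Φ{[√n·(p2 − p1) − z·√(2p̄(1 − p̄))] / √(p1(1 − p1) + p2(1 − p2))}, with p̄ = (p1 + p2)/2.

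74% versus 99%, two-sided (z = 1.96):
- p̄ = 0.865; √(2 × 0.865 × 0.135) = 0.4833; √(0.1924 + 0.0099) = 0.4498
- (√30 × 0.25 − 1.96 × 0.4833)/0.4498 = (1.3693 − 0.9472)/0.4498 = 0.938, so power = 82.6%
- Solved for 80% power: n = [(1.96 × 0.4833 + 0.8416 × 0.4498)/0.25]² = 28.1, so 29 per arm, 58 in total

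That is close to the planned 60. At the midpoint (96.5%) the one-sided version gives 80.4%. So the plan's figure can be obtained, but only in the upper part of the range.

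**The same formula at the 20-point end.** 74% versus 94%:
- p̄ = 0.84; √(2 × 0.84 × 0.16) = 0.5185; √(0.1924 + 0.0564) = 0.4988
- Two-sided: (1.0954 − 1.96 × 0.5185)/0.4988 = 0.159, so power = 56.3%
- One-sided: (1.0954 − 1.645 × 0.5185)/0.4988 = 0.486, so power = 68.7%
- For 80% power: 52 per arm two-sided, 41 one-sided

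**Exact power of the planned test.** Every pair of success counts (0 to 30 in each arm) was enumerated, weighted by its two binomial probabilities, and counted when the test rejects.

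| Method, 30 per arm, 5% level | 88.8% | 92.5% | 94% | 99% |
|---|---|---|---|---|
| Two-sided, planned rule, observed cells | 20.7% | 34.7% | 42.2% | 74.7% |
| Two-sided, planned rule, expected counts | 27.6% | 42.1% | 48.8% | 75.3% |
| Two-sided, normal formula | 31.0% | 48.3% | 56.3% | 82.6% |
| Two-sided, uncorrected chi-square, exact | 31.2% | 50.4% | 59.8% | 92.3% |
| One-sided, planned rule, observed cells | 30.8% | 47.2% | 55.3% | 85.6% |
| One-sided, planned rule, expected counts | 39.8% | 54.6% | 61.0% | 85.7% |
| One-sided, normal formula | 43.1% | 61.1% | 68.7% | 89.9% |
| One-sided, uncorrected chi-square, exact | 45.5% | 65.0% | 73.2% | 96.5% |

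The first two columns are the relative reading, the last two the absolute reading.

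**Which rows describe the plan.** The probability that at least one observed cell is below 5, so that Fisher applies, is 97.1% at 94% and above 99.9% at 99%. The observed-cell rows are therefore almost the power of Fisher alone (42.1% two-sided and 55.1% one-sided at 94%). At the midpoint of 96.5% the observed-cell rule gives 56.9% two-sided and 70.0% one-sided.

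**What 80% would require.** With 30 per arm, CSE success would have to reach 99.7% (two-sided, observed-cell rule), 98.2% (one-sided, same rule), 97.0% (two-sided chi-square) or 95.3% (one-sided chi-square). All exceed 94%. At 74% versus 94%, the observed-cell rule needs 55 per arm two-sided (80.7%) or 45 one-sided (80.8%).

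**The case against.** The strongest reply is that alpha is not stated, so the shortfall depends on assuming 5%. At a one-sided 10% level, 74% versus 94% gives 80.6% by the normal formula and 83.6% by exact chi-square. This stands as a limit on the claim: the conclusion is for a 5% level. It does not rescue the sentence, because nothing in the documents points to 10%, and even there the planned rule gives only 73% (observed cells) or 78% (expected counts).

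Second, the 80% is not baseless. It can be reproduced near 99% two-sided or near the midpoint one-sided, and the sentence speaks of a difference without tying it to 20 points. That is fair, and the likeliest error is that an upper-end calculation was quoted for the whole range. But the conclusion is drawn directly from the 20-25% statement, so it should be true at 20.

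Third, the 42-73% span mixes tests, and its top comes from an uncorrected chi-square that would rarely be used. This is correct: for the planned rule alone the span is 42-61%. The wider span is given only to show that no choice of method at 5% reaches 80%.

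Fourth, this is a pilot whose size was taken as given. A pilot need not be powered for efficacy. This one, however, states a null and a directional alternative, plans a significance test of the primary outcome, and makes an explicit power claim.

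**Conclusion.** The concern holds. As written, 80% power is not supported across the stated range. For a true gain from 74% to 94%, the planned test has 42-49% power two-sided or 55-61% one-sided, depending on how the small-cell rule is read. With the two-sided observed-cell rule, a 20-point gain would be missed about 58% of the time, not 20%, and power stays below 80% even at 99% (75%). One-sided, that rule passes 80% only from 98.2% upward. If the gain is relative, no method in the table reaches 80% anywhere in the range.

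This rests on equal allocation, a 5% level, no dropout and 74% in the epidural arm. Any dropout would lower these figures further.

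**What to change.** Replace the power sentence. State alpha, sidedness, 1:1 allocation, whether the 20-25% gain is absolute or relative, and whether the small-cell rule refers to observed or expected counts. Then give the power of that test at both ends of the range. For absolute points and observed cells, suitable wording would be:

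- *Two-sided:* With 30 women per arm, an assumed 74% success rate in the epidural arm and a two-sided 5% level, power is about 42% if CSE success is 94% and 75% if it is 99%.
- *One-sided:* the corresponding figures are about 55% and 86%.

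Describe the 20-25% gain as an assumption carried over from studies outside TOLAC, since the Background says none were done in that population.

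Two reporting additions would help, though correcting the figure does not depend on them. Report the risk difference with a 95% confidence interval, and say that non-significance will not be read as no difference. As a rough guide to precision, the Wald half-width 1.96 × √[(0.1924 + p2(1 − p2))/30] is about 22 points at 74% in both arms, 18 at 94% and 16 at 99%. Wald is unreliable at the top end, where the chance of no CSE failures is 0.99³⁰ = 74%, so name an interval method that copes with empty cells.

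The cost is the rewording of one paragraph and a less favourable stated power. The sample size, endpoint and test can stay as they are.
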